4.1.3.2. Technical factors

Treatment shall be delivered using the Trilogy[™] Linear Accelerator (Varian Medical Systems, Palo Alto, CA) or the CyberKnife[™] Robotic Radiosurgery System (Accuray, Sunnyvale, CA).

4.1.3.3.Localization, simulation, and immobilization

The patient shall be treated in the supine position. An aquaplast head mask will be used to ensure adequate immobilization during therapy. The target volume shall be either the resection cavity or the unresectable lesion. When the resection cavity is targeted, a uniform isotropic 2 mm expansion of the cavity will be the target volume[17].

4.1.3.4.Critical structures

Critical normal structures (e.g., optic apparatus, brain stem) will be contoured and their doses minimized. The patient will be excluded from the protocol if the tumor's proximity to critical structures is such that a dosimetrically acceptable plan is not achievable to conform to these constraints.

4.2 General Concomitant Medication and Supportive Care Guidelines

Supportive treatment may include anti-emetics, anti-diarrheal medications, antipyretics, anti-histamines, analgesics, antibiotics, and others, such as blood products. Patients will be permitted to receive appropriate supportive care measures as deemed necessary by the treating physician.

Steroids may be given after each SRS treatment to decrease the risk of CNS symptoms due to cerebral edema. In addition, steroids may be used as required to control CNS symptoms due to tumor-associated or RT-associated cerebral edema, but wherever possible, should be tapered and stopped.

Nausea/vomiting: Nausea and vomiting should be treated aggressively. In particular, the use of antiemetics including 5HT3 antagonists and/or dexamethasone is encouraged. Patients should be strongly encouraged to maintain liberal oral fluid intake during therapy.

4.3 **Duration of Therapy**

SRS will be given in 3 fractions, each approximately 24 hours apart.

4.4 **Duration of Follow Up**

Follow-up schedule is summarized in section 9. Study Calendar.

Patients will be seen in follow-up at 1st, 3rd, 6th, 9th, and 12th months following radiation. The following will be obtained at pre-treatment evaluation and at each follow-up time point: Neurologic history and physical examination, KPS, steroid use assessment, and toxicity evaluation. MRI with gadolinium will be obtained at pre-treatment and at 3, 6, 9, and 12 months following treatment until progression is documented and continuing every 3 months for those without evidence of intracranial progression.

After the first 12 months, patients will be followed every 3-6 months at the discretion of the patient's physician. At each visit, interval history, physical exam, KPS, toxicity evaluation, and brain MRI scans will be obtained.

For those subjects who are unable to come for clinic visits, clinical follow-up information will be obtained via 1) a phone call to the patient and/or 2) clinic source document from his/her local physician. For subjects unable to appear in person for clinic visits, HRQOL questionnaires will be completed via a telephone interview or mail.

For patients unable to return for imaging studies, source documents from outside institutions will be used to document imaging follow-up.

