4.5 Criteria for Removal from Study

- Disease progression or death
- Intercurrent illness that prevents further administration of treatment: a condition, injury, or disease unrelated to cancer, that renders continuing of radiation treatment unsafe or regular study visits impossible.
- Unacceptable adverse event(s) (see adverse events)
- Patient decides to withdraw from the study
- General or specific changes in the patient's condition that render the patient ineligible for the study
- Non-compliance with protocol-required evaluations and study visits
- Inability of subject to comply with study requirements
- Determination by the investigator that it is no longer safe for the subject to continue therapy
- Patients who inadvertently become pregnant
- At the discretion of the treating investigators

Subjects who are discontinued from the study will still be followed for disease progression and survival.

Subjects who discontinue should, if possible, be seen and assessed by an investigator(s). The reason for withdrawal and the date of withdrawal must be documented.

If the reason for withdrawal from the trial is the death of the subject, the two options for categorizing withdrawal are either progressive disease or an adverse event (AE; more than one AE may be documented as a reason for withdrawal). Only one event will be captured as the cause of death. Note that death is an outcome and not an AE.

All trial treatment-related toxicities and serious adverse events (SAEs) must be followed up until resolution.

At withdrawal, all on-going study-related toxicities and SAEs must be followed until resolution, unless in the investigator's opinion, the condition is unlikely to resolve due to the subject's underlying disease.

Subjects/patients who discontinue from the study for reasons unrelated to the study (e.g., personal reasons, or adverse events after registration but prior to receiving study therapy) may be replaced as required for the study to meet its objectives. The decision

to remove a subject/patient and to replace dropouts will be made by the treating investigator. The replacement will generally receive the same treatment or treatment sequence (as appropriate) as the allocation number replaced.

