10. MEASUREMENT OF EFFECT

10.1 Anti-tumor Effect

Subjects will be seen in follow-up at 1, 3, 6, 9, and 12 months following SRS.At each follow-up, neurologic history and examination will be done. MRI with gadolinium will be obtained at 3, 6, 9, and 12 months.

10.1.1 **Definitions**

Early radiation toxicity is defined as those observed within 30 days of SRS. Late radiation toxicity is defined as those observed after 30 days following SRS. Tumor response will be measured using MRI with gadolinium obtained at 3, 6, 9 and 12 months following SRS.

10.1.2 **Disease Parameters**

Target lesion is defined as those treated with radiosurgery. The size and volume of the target lesion will be measured using the treatment planning software.

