10.1.4.1 Evaluation of Target Lesions

Radiographic response using MRI with gadolinium will be used. Follow-up MRI scans will be obtained at 3, 6, 9, and 12 months following SRS. Size of the treated lesion will be measured and compared to its pre-treatment size. Local tumor progression is defined as the radiographic appearance of a new or increasing enhancing lesion within the radiosurgical target volume. Local control is defined as lack of progression (P – below). Metabolic imaging may be necessary at times to distinguish tumor progression from treatment related radiation necrosis.

- 4.1.3.4.1. Complete response (CR): The tumor is no longer seen on the follow-up MRI scan.
- 4.1.3.4.2. Partial response (PR): Decrease of >50% in the product of two diameters on the follow-up MRI scan.

- 4.1.3.4.3. Minor response (MR): Decrease of <50% in the product of two diameters on the follow-up MRI scan.
- 4.1.3.4.4. Stable disease (SD): The scan shows no change.
- 4.1.3.4.5. Progression (P): A >25% increase in tumor area (product of two diameters).

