10.1.4.2 Evaluation of Non-Target Lesions

The distant control rate will be determined. Distant brain failure is defined as the radiographic appearance of a new or enhancing lesion more than 5 mm from the radiosurgical target volume[19]. Elsewhere brain failure rate will be determined using MRI scanning with gadolinium obtained at 3, 6, 9, and 12 months following SRS.

10.1.4.3 **Evaluation of Best Overall Response**

N/A

10.1.5 **Duration of Response**

N/A

10.1.6 **Progression-Free Survival (or other parameters)**

Time to progression will be measured from the time of SRS. Overall survival will be measured from 1) the time of diagnosis, and 2) time of SRS.

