12.1.2 Secondary endpoints

- 12.1.2.1.To determine the local control rate of fractionated SRS for brain metastases $4.2 14.1 \text{ cm}^3$ and $14.2 33.5 \text{ cm}^3$.
- 12.1.2.2.To determine the distant brain control rate of fractionated SRS for brain metastases 4.2 14.1 cm³ and 14.2 33.5 cm³.
- 12.1.2.3.To determine the overall survival rate of fractionated SRS for brain metastases 4.2 14.1 cm³ and 14.2 33.5 cm³.

- 12.1.2.4.To determine the short- and long-term adverse effects of fractionated SRS for brain metastases 4.2 14.1 cm³ and 14.2 33.5 cm³.
- 12.1.2.5.Patient health related quality of life will be assessed using the EORTC QLQ-C30 and EORTC Brain Cancer Module QLQ-BN20.

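### Read literally, section 4.4 ends scheduled MRI at any intracranial progression, so local failure after a distant-only failure has no assured imaging through month 12

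*Combined protocol and SAP*

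**What the plan says.** Section 4.4 is the only place that gives a stop condition for MRI. Scans are due before treatment and at 3, 6, 9 and 12 months "until progression is documented and continuing every 3 months for those without evidence of intracranial progression". After month 12 the same section sets visits every 3 to 6 months and attaches no progression condition to imaging: "At each visit, interval history, physical exam, KPS, toxicity evaluation, and brain MRI scans will be obtained". It also accepts imaging records from outside institutions, but only for patients who cannot come back for scans.

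Section 4.5 lists "Disease progression or death" as a ground for removal, without naming a site of progression. It then adds: "Subjects who are discontinued from the study will still be followed for disease progression and survival". It gives no imaging schedule for that follow-up.

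The study calendar in section 9 marks MRI at all four time points with no stop. Section 10.1 agrees: "MRI with gadolinium will be obtained at 3, 6, 9, and 12 months". Sections 10.1.3, 10.1.4.1 and 10.1.4.2 repeat those time points.

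Local and distant failure are different events. In 10.1.4.1, "Local control is defined as lack of progression", where local progression is judged within the radiosurgical target volume. In 10.1.4.2, "Distant brain failure is defined as the radiographic appearance of a new or enhancing lesion more than 5 mm from the radiosurgical target volume". Section 12.1.2 lists them as separate secondary endpoints, the first being "To determine the local control rate of fractionated SRS for brain metastases". No section gives an estimator, a landmark time or a censoring rule for local control, or says how death or salvage treatment is handled.

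**The concern.** Under the literal reading of 4.4, one endpoint event ends scheduled observation of another. A patient with a distant-only failure at month 3 has no assured scan of the treated cavity at 6, 9 or 12 months. Because local control means absence of progression, and no censoring rule is given, that patient can be counted as controlled without having been imaged. If the patient is censored instead, the analysis assumes that distant failure says nothing about the risk of local failure.

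Local control is the first-listed secondary endpoint, and the synopsis hypothesis is that fractionation improves it. Target scans that were never collected cannot be recovered at analysis.

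**Working it through.** **Nothing to reproduce.** The documents state no target, precision or sample size for local control. The check therefore compares imaging continued after distant failure with imaging stopped at the first intracranial progression.

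**Inputs from the documents**
- 12-month local control 79% (section 2.4, the institution's retrospective actuarial figure), used as the illustrative truth.
- Median survival 10 or 16 months (ends of the range in section 2.1), taken as exponential.
- MRI at 3, 6, 9 and 12 months (sections 4.4, 9 and 10).

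**Assumptions not in the documents**
- 12-month distant brain failure of 30%, 45% or 60%.
- Local and distant failure either independent or positively correlated through a shared gamma frailty of variance 0.5 or 1.0, with both marginal rates held fixed.

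**Method.** Simulation of 400,000 patients per scenario. A failure is detected at the first scan on or after it occurs, if the patient is alive. Under the stop rule, a local failure counts as seen only if it is detected no later than the scan that shows the distant failure. Three estimators were compared:
1. Crude: 1 minus the proportion of all patients with an observed local failure.
2. Kaplan-Meier censored at the last MRI.
3. Kaplan-Meier with unscanned patients carried forward as controlled until death or month 12.

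**With imaging continued.** Kaplan-Meier returns about 79% in every scenario. The crude proportion is already 84-87%, because patients who die without an observed local failure count as controlled.

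**With imaging stopped.** The table shows the share of otherwise detectable local failures that go unseen, and the change in 12-month local control in percentage points. Each cell gives median survival 10 / 16 months.

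| Distant failure | Dependence (frailty variance) | Unseen | Crude | KM, censored | KM, carried forward |
|---|---|---|---|---|---|
| 30% | none | 10% / 10% | +1.3 / +1.6 | +0.1 / 0.0 | +2.5 / +2.4 |
| 30% | 0.5 | 13% / 14% | +1.7 / +2.1 | +1.1 / +1.2 | +3.3 / +3.3 |
| 30% | 1.0 | 16% / 17% | +2.1 / +2.6 | +2.1 / +2.0 | +4.0 / +3.9 |
| 45% | none | 15% / 16% | +2.0 / +2.5 | +0.1 / 0.0 | +3.9 / +3.8 |
| 45% | 0.5 | 20% / 22% | +2.6 / +3.4 | +1.8 / +1.8 | +5.1 / +5.1 |
| 45% | 1.0 | 25% / 27% | +3.3 / +4.2 | +3.4 / +3.5 | +6.2 / +6.3 |
| 60% | none | 21% / 23% | +2.8 / +3.5 | 0.0 / 0.0 | +5.3 / +5.3 |
| 60% | 0.5 | 29% / 31% | +3.8 / +4.8 | +2.9 / +2.9 | +7.2 / +7.2 |
| 60% | 1.0 | 35% / 37% | +4.6 / +5.8 | +5.1 / +5.1 | +8.6 / +8.7 |

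Example (60%, variance 1.0, median 16 months): the crude rate goes from 84.4% to 90.2%, a change of 5.8 points. Censored Kaplan-Meier goes from 79.0% to 84.1%, and carried-forward Kaplan-Meier from 79.0% to 87.7%.

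**Scale.** With the 30 evaluable patients that section 12.3.1 gives as the maximum per arm, the binomial standard error at 79% is sqrt(0.79 × 0.21 / 30) = 0.074, or 7.4 points.

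**The case against.** **The documents do not say that looking stops.** A reader might infer that local failure after a distant failure is simply not looked for. Section 4.5 keeps discontinued subjects under follow-up for progression, sections 9 and 10 schedule MRI with no stop, and 4.4 itself requires MRI after month 12 regardless of progression. This stands: the defect is a conflict between sections and an undefined imaging schedule after progression, not a settled absence of follow-up. It does not remove the point. Only 4.4 states a stop, 4.5 gives no schedule, and MRI resumed after month 12 cannot fill the earlier gap.

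**The stop condition is ambiguous.** Progression as a response category is defined only for the treated target (10.1.4.1), and distant events are called failures. The first half of the 4.4 sentence could therefore mean target progression. That is a fair reading, but the second half refers to intracranial progression, which a distant lesion satisfies. Sites could apply either.

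**The bias is not certain.** A reader might infer that the local control rate is necessarily too favourable. No estimator is named, and the only precedent in the documents (section 2.4) is actuarial. Censored at the last MRI, that estimate is unbiased if the two failures are independent. This stands. The crude and carried-forward rates can only rise, but the censored rate moves upward only under positive correlation. Negative correlation was not simulated.

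**The size is easily overstated.** With independent constant hazards and no deaths, observed local failure at 12 months is hL/(hL+hD) × (1 − exp(−12(hL+hD))), with hL = −ln(0.79)/12. For assumed distant failure of 30%, 50% and 70% this gives 0.178, 0.154 and 0.125 against 0.21. A reader might infer local control of 82%, 85% or 88% instead of 79%. That sets a crude rate that ignores death against an actuarial one. Once death is included, the crude rate is 84-87% even with full imaging, and the stop rule adds 1.3 to 5.8 points.

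**Importance.** Local control is one of five secondary endpoints, and most of the shifts are smaller than the 7.4-point standard error. That is true, but this error does not shrink with more patients and a confidence interval would not show it.

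**Conclusion.** The point holds as an inconsistency with a likely bias. Read literally, 4.4 lets a distant-only failure end assured target imaging through month 12, against sections 9, 10 and 4.5 and against the separation of local and distant endpoints.

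If 4.4 is followed, about 10-37% of detectable local failures go unseen. The 12-month local control rate is then likely too high by about 1 to 6 points (crude), about 2.5 to 9 points (carried forward as controlled), or about 1 to 5 points (censored Kaplan-Meier with positive correlation), and by 0 points for the censored analysis under independence. These sizes rest on the assumed 30-60% distant failure and frailty variances, and on the illustrative 79% control and 10 to 16 month median survival.

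The documents support neither a claim that local failure is definitely not sought nor one that the rate is definitely inflated. The MTD rests on DLTs within 30 days of radiosurgery and is not affected.

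**What to change.** 1. Reconcile 4.4, 4.5, 9 and 10 so that target-site imaging data are collected until local progression or 12 months, including after a distant-only failure.
2. Use routine clinical or outside MRI for this, and read the target volume on it. Extend the 4.4 allowance for outside records to patients who have progressed, so that no procedure is added.
3. In section 12, estimate local control by time-to-event methods from SRS, censored at the last target-site MRI, with the time point stated.
4. State how death and salvage whole-brain treatment are handled. Section 2.4 describes whole-brain radiation as deferred for salvage, so without a rule its effect on the target could be credited to SRS.
5. Report how many patients have no target imaging after a distant failure.

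The cost is protocol wording and some extra record collection for progressed patients, with no additional patients. The downside is that scans after salvage treatment are hard to interpret without the rule in item 4.

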4.5 Criteria for Removal from Study

- Disease progression or death
- Intercurrent illness that prevents further administration of treatment: a condition, injury, or disease unrelated to cancer, that renders continuing of radiation treatment unsafe or regular study visits impossible.
- Unacceptable adverse event(s) (see adverse events)
- Patient decides to withdraw from the study
- General or specific changes in the patient's condition that render the patient ineligible for the study
- Non-compliance with protocol-required evaluations and study visits
- Inability of subject to comply with study requirements
- Determination by the investigator that it is no longer safe for the subject to continue therapy
- Patients who inadvertently become pregnant
- At the discretion of the treating investigators

Subjects who are discontinued from the study will still be followed for disease progression and survival.

Subjects who discontinue should, if possible, be seen and assessed by an investigator(s). The reason for withdrawal and the date of withdrawal must be documented.

If the reason for withdrawal from the trial is the death of the subject, the two options for categorizing withdrawal are either progressive disease or an adverse event (AE; more than one AE may be documented as a reason for withdrawal). Only one event will be captured as the cause of death. Note that death is an outcome and not an AE.

All trial treatment-related toxicities and serious adverse events (SAEs) must be followed up until resolution.

At withdrawal, all on-going study-related toxicities and SAEs must be followed until resolution, unless in the investigator's opinion, the condition is unlikely to resolve due to the subject's underlying disease.

Subjects/patients who discontinue from the study for reasons unrelated to the study (e.g., personal reasons, or adverse events after registration but prior to receiving study therapy) may be replaced as required for the study to meet its objectives. The decision

to remove a subject/patient and to replace dropouts will be made by the treating investigator. The replacement will generally receive the same treatment or treatment sequence (as appropriate) as the allocation number replaced.

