1.2. Secondary Objectives

- 1.2.1. Determine the local control rate as assessed on MRI and clinical exam.
- 1.2.2. Determine short- and long-term adverse effects.
- 1.2.3. Determine the distant intra-cranial control rate.
- 1.2.4. Determine the overall survival rate.
- 1.2.5. Assess the patient's health related quality of life.

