10.2 Other Response Parameters

The primary endpoint of this study is to determine the MTD of tri-fraction SRS. The MTD is defined as one dose level below the highest toxic dose (i.e., the DLT dose). Similar to RTOG 90-05, the dose limiting toxicity (DLT) is defined as grade 3, 4, or 5 RTOG central nervous system (CNS) acute radiation morbidity scoring criteria (Appendix C) observed within 30 days of radiosurgery.

The occurrence of late toxicities will be continuously monitored. If a late DLT occurs in 3 or more out of 6 (or 4 or more out of 12) patients at a certain dose level after the radiation dose had already been escalated to the next level, the MTD will be backtracked to the level

below the one at which the DLTs occurred.

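### Section 4.5 removes patients at any disease progression and names progression and survival as the continuing follow-up, in conflict with the late-toxicity follow-up in 4.4, Section 9, 10.2 and 11.2

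*Combined protocol and SAP*

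**What the plan says.** Section 4.5 lists "Disease progression or death" first among the criteria for removal and does not restrict progression to the treated lesion or to the brain. For what happens next it states: "Subjects who are discontinued from the study will still be followed for disease progression and survival". Two further sentences in 4.5 concern safety. One is general: "All trial treatment-related toxicities and serious adverse events (SAEs) must be followed up until resolution". The other covers events present when the patient leaves: "At withdrawal, all on-going study-related toxicities and SAEs must be followed until resolution", with an exception where the underlying disease makes resolution unlikely.

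Section 4.4 requires the following at months 1, 3, 6, 9 and 12: "Neurologic history and physical examination, KPS, steroid use assessment, and toxicity evaluation". It makes only the MRI depend on progression: "until progression is documented and continuing every 3 months for those without evidence of intracranial progression". After month 12 it keeps toxicity evaluation at every visit. The Section 9 calendar shows toxicity and QOL evaluation through month 12 with no progression condition.

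Sections 4.1.3.1, 10.2 and 11.2 each say: "The occurrence of late toxicities will be continuously monitored". Each then moves the MTD down if a late DLT occurs in at least 3 of 6, or at least 4 of 12, patients at a dose level. Section 10.1.1 defines late as after 30 days and gives no upper limit. Objective 1.2.2 is "Determine short- and long-term adverse effects", and objective 1.2.5 is quality of life.

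**The concern.** Section 4.3 gives the treatment as three fractions about 24 hours apart. It will be finished before progression in almost every patient, so removal at progression acts almost entirely on follow-up. A patient whose extracranial disease progresses at month 2 meets the 4.5 criterion although the treated site is unchanged. The late toxicities listed in 7.1.2, such as radiation necrosis, focal deficits and memory difficulties, can first appear well after that.

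The backtracking rule counts patients with a late DLT against a fixed 6 or 12. A patient who is no longer assessed stays in the denominator and cannot add to the numerator, so any bias runs toward keeping the dose.

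The loss may also be related to the toxicity itself. Section 10.1.4.1 defines local progression by new or increasing enhancement and accepts that metabolic imaging may be needed to tell tumour from necrosis. A patient whose enhancement is first read as progression can therefore be removed just when necrosis is in question.

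**Working it through.** **1. Does toxicity evaluation continue after progression?**

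| Place | What it implies |
|---|---|
| 4.5, removal criteria | Progression at any site removes the patient |
| 4.5, follow-up after discontinuation | Progression and survival are named; toxicity, KPS, steroids and QOL are not |
| 4.5, safety sentences | Toxicities and SAEs are followed to resolution; no schedule for detecting new ones |
| 4.4 and Section 9 | Toxicity, KPS and steroid assessment (and QOL in Section 9) at fixed months, with no progression condition |
| 4.1.3.1, 10.2, 11.2 | Late toxicity monitored continuously; progressed patients not excluded |

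Under 4.5, a new late event after progression has no scheduled assessment. Under 4.4, it does. No passage says which governs.

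**2. Direction.** Let p be the true late-DLT rate and m the share of late DLTs that first arise after removal and are not captured. The recorded rate is q = p(1 - m), which is never above p. The denominator does not change, so the chance of triggering can only fall.

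**3. Illustration of size.** The plan states no late-DLT rate and no operating characteristic for this rule, so there is no figure to reproduce. Both p and m are assumptions. Section 2.4 reports 79% local control at 12 months in a retrospective series, so local failure is 1 - 0.79 = 0.21. That is a proportion of patients, not a share of late DLTs, and serves only as one point in the range of m. No distant-brain or systemic progression rate is given.

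Formulas: P(X >= 3) with X ~ Bin(6, q), and P(X >= 4) with X ~ Bin(12, q).

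Worked case, p = 0.40 and m = 0.40, so q = 0.40 x 0.60 = 0.24:
- 12 patients: 1 - (0.0371 + 0.1407 + 0.2444 + 0.2573) = 0.320. With full capture (q = 0.40): 1 - (0.0022 + 0.0174 + 0.0639 + 0.1419) = 0.775.
- 6 patients: 1 - (0.1927 + 0.3651 + 0.2882) = 0.154. With full capture: 1 - (0.0467 + 0.1866 + 0.3110) = 0.456.

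Chance that the rule triggers:

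| p | Patients | m = 0 | m = 0.21 | m = 0.40 | m = 0.60 |
|---|---|---|---|---|---|
| 0.20 | 6 | 0.099 | 0.054 | 0.026 | 0.009 |
| 0.20 | 12 | 0.205 | 0.107 | 0.046 | 0.012 |
| 0.30 | 6 | 0.256 | 0.149 | 0.076 | 0.026 |
| 0.30 | 12 | 0.507 | 0.311 | 0.155 | 0.046 |
| 0.40 | 6 | 0.456 | 0.286 | 0.154 | 0.056 |
| 0.40 | 12 | 0.775 | 0.556 | 0.320 | 0.111 |
| 0.50 | 6 | 0.656 | 0.445 | 0.256 | 0.099 |
| 0.50 | 12 | 0.927 | 0.764 | 0.507 | 0.205 |

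The m = 0 column is what 4.4, applied literally with every event found, would give.

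**The case against.** A reader might infer that patients are followed only for progression and survival after removal, so that new late toxicity is not collected and the results are biased. The documents do not support that. The word 'only' is not in 4.5, and no sentence ends toxicity, KPS, steroid or QOL assessment at progression. Section 4.4 ties the MRI to progression and nothing else, which suggests that its authors wrote such a condition where they meant one. The general sentence in 4.5 on following toxicities and SAEs is not limited to events present at withdrawal. Adverse event reporting in 7.2.2 has no cut-off at removal, and many severe late CNS events would meet the SAE definition in 7.2.1.

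The size is also open. Time to any progression, the late-DLT rate and the share of events missed are all assumed. At p = 0.40 the 3-of-6 rule triggers less than half the time (0.456) even with full capture, so its weakness does not come mainly from 4.5. Acute escalation decisions use a 30-day window and are largely unaffected.

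These points limit the claim to a conflict and a possible bias. They do not remove it. A duty to follow or report known events is not a schedule for finding new ones, and the sentence naming progression and survival would have little purpose if all Section 9 visits continued anyway. Even under 4.4 the scheduled first-year MRI runs until progression is documented, so necrosis visible only on imaging could still be missed.

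**Conclusion.** The conflict is real: whether late toxicity must be sought after progression depends on which section is followed. It bears on the late-toxicity check of the MTD and on objectives 1.2.2 and 1.2.5. If events are missed, the direction is certain for the backtracking count, while the long-term toxicity and QOL summaries may look too favourable.

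The size cannot be determined from the documents. The fall at p = 0.40 with m between 0.21 and 0.40 (0.775 to 0.556-0.320 for 12 patients, 0.456 to 0.286-0.154 for 6) rests wholly on assumed p and m. It also treats patients as independent with a common rate. It shows only that a modest loss would matter to a rule this small. This should be fixed; confidence is moderate because the plan can be read so that nothing is lost.

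**What to change.** Reconcile 4.5 with 4.4, Section 9, 10.2 and 11.2. Suggested wording for 4.5: 'Patients removed for disease progression will continue toxicity evaluation, steroid use assessment, KPS and QOL at the Section 9 time points, in person or by the remote routes in 4.4, and will be followed for progression and survival, unless they withdraw consent.'

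Record the date of any later brain radiation, and report late toxicity with and without events after that date. State in 10.2 and 11.2 which of these counts feeds the backtracking rule.

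The cost is a short amendment. The visits are already scheduled, and 4.4 already allows telephone, mail and outside records. The downside is that events after progression or further brain treatment are harder to attribute. The two-way report shows how much this matters but does not resolve it.
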